- 11. Subject has untreated or uncontrolled hypothyroidism
- 12. Known or suspected intolerance or hypersensitivity to the investigational product(s) or allopregnanolone, or any of the stated ingredients
- 13. Use of another investigational product within 60 days prior to the first dose of investigational product
- 14. Has alanine transferase (ALT) or aspartate transferase (AST) greater than 2.5 times upper limit of normal or total bilirubin greater than 1.5 times upper limit of normal (unless elevation is due to Gilbert's syndrome)
- 15. Screening QTcF > 470 msec
- 16. Unwillingness to withhold grapefruit, Seville oranges, star fruit, or citrus derived products from diet between screening and discharge from the study unit
- 17. Receiving concomitant treatment with strong CYP3A4 inducers or strong CYP3A4 inhibitors
- 18. Body mass index (BMI)  $\ge 40$
- 19. Subject is pregnant
- 20. Subject is using prohibited medications as specified in Section 5.3.2

Maximum duration of subject involvement in the study: Approximately 12 weeks

**Safety:** Adverse events, vital signs, Columbia Suicide Severity Rating Scale (CSSRS), electrocardiogram (ECG), Stanford Sleepiness Scale (SSS), and physical examination.

**Efficacy:** Hamilton Depression Rating Scale (HAMD17), Edinburgh Postnatal Depression Scale (EPDS), Spielberger State-Trait Anxiety Inventory six item version (STAI6) and Clinical Global Impression-Improvement (CGI-I) scale.

**Pharmacokinetics:** Six samples will be collected for pharmacokinetic analysis in Cohorts 1-5 and 12 samples in Cohort 6. Maximal plasma concentration ( $C_{max}$ ), concentration at steady-state ( $C_{ss}$ , determined by the mean concentrations once steady-state is achieved by visual inspection), AUC0-24 (calculated as  $C_{ss}$  multiplied by 24 hours) will be estimated. Seven samples will be collected during the inpatient phase of Cohort 6 (including 6 samples on Day 1) followed by collection of 5 samples during the outpatient phase during the study visits for a total of 12 samples in Cohort 6.

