#### 4.1 Inclusion Criteria

The subject will not be considered eligible for the study without meeting all of the criteria below.

- 1. An understanding of and ability, and willingness to fully comply with study procedures and restrictions.
- 2. Ability to voluntarily provide written, signed, and dated informed consent as applicable to participate in the study.
- 3. Female aged 18 to 45 years, inclusive, at the Screening Visit
- 4. Experiencing a Major Depressive Episode, which started between the start of the third trimester and 4 weeks following delivery. The Major Depressive Episode must be diagnosed according to MINI 7.0 interview
- 5. Given birth in the last 12 months
- 6. HAMD17 score of  $\geq$  26 at screening (HAMD17 must be  $\geq$  22 per CTNI rating at Admission to the Unit on Day 0)
- 7. The diagnosis of PPD and severity of depression must be supported by the SAFER interview
- 8. Must agree to stop breastfeeding from start of study treatment to 45 days after end of study treatment
- 9. Must agree to use acceptable contraceptive methods during the study period

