- 10. Any clinically significant abnormality identified on physical examination, ECG or laboratory tests, that in the judgment of the investigator would compromise the subject's safety or successful participation in the clinical study
- 11. Subject has untreated or uncontrolled hypothyroidism
- 12. Known or suspected intolerance or hypersensitivity to the investigational product(s) or allopregnanolone, or any of the stated ingredients
- 13. Use of another investigational product within 60 days prior to the first dose of investigational product
- 14. Has alanine transferase (ALT) or aspartate transferase (AST) greater than 2.5 times upper limit of normal or total bilirubin greater than 1.5 times upper limit of normal (unless elevation is due to Gilbert's syndrome)
- 15. Screening QTcF > 470 msec
- 16. Unwillingness to withhold grapefruit, Seville oranges, star fruit, or citrus derived products from diet between screening and discharge from the study unit
- 17. Receiving concomitant treatment with strong CYP3A4 inducers or strong CYP3A4 inhibitors
- 18. Body mass index  $(BMI) \ge 40$
- 19. Subject is pregnant
- 20. Subject is using prohibited medications as specified in Section 5.3.2

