#### 5.3.1.3 Other Permitted Treatments

The subject may continue her current non-psychiatric medications with the exception of medications that are strong inducers or inhibitors of CYP3A4 (Appendix 1).

The subject may use diphenhydramine 25 to 50 mg, trazodone 25 to 50 mg or doxepin 3 to 5 mg during the inpatient or outpatient phase for severe insomnia as needed. Only 1 dose of 1 of the medications is allowed per night. It is recommended to use the same medication each night. To minimize carryover effects there should be a minimum of 10-hour interval between administration of an allowed hypnotic and any efficacy assessment. Other hypnotics, such as zolpidem or zaleplon, are prohibited.

If the subject is treated with an atypical antipsychotic medication that was started with the purpose of augmenting the therapeutic effect of an antidepressant (i.e. the antipsychotic is not intended for treatment of psychosis or mood stabilization), she may continue this treatment throughout the study period. Examples of such treatments would be quetiapine 50 mg at bedtime and aripiprazole 15 mg daily. However, the antipsychotic medication must have been started at least 21 days before the screening, and there should not have been a dose change within 7 days of screening.

Other medications and medication combinations should be discussed with the medical monitor before enrolling the subject in the study.

After the subject completes the study treatment period, any changes to the antidepressant or antianxiety medication regimen are not prohibited, but investigators are encouraged to maintain such drugs at stable doses if possible. Any changes in the medication regimen must be recorded on the concomitant medication eCRF page.

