#### 5.3.2 **Prohibited Treatments**

The following classes of medications and treatments are prohibited during the study treatment period. If the subject has been taking any of these medications before enrollment, there should be a medication-free period of a minimum of 5 days or 5 half-lives of that medication, whichever is longer, before admission to the unit. In general, subjects who require extensive washouts may not be candidates for participation and those cases should be discussed with the medical monitor.

- Benzodiazepines and barbiturates
- Gabapentin and pregabalin
- Anticonvulsants and mood stabilizers
- All hypnotics and sleep aids (with the exception of low-dose diphenhydramine, doxepin, and trazodone as described above)
- Opioids

- Cannabis
- Electroconvulsive Therapy (ECT), rapid transcranial magnetic stimulation (rTMS), vagal nerve stimulation
- Experimental (including hormonal and herbal) treatments of postpartum depression
- Strong inhibitors and inducers of CYP3A4 (Appendix 1)

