## 7.6.7 Visit 8 (Day +29 ±3 days)

• CTNI to conduct HAMD17 interview

- EPDS
- STAI6
- Assess CGI-I
- Review concomitant medications and therapies
- Collect vital signs (BP, pulse, temperature, pulse oximetry, respiratory rate),
- Collect ECG
- Collect urine sample for urinalysis, drug screen and urine pregnancy test
- Collect safety laboratory tests
- Collect a pharmacokinetic sample
- Measure weight
- Stanford Sleepiness Scale (SSS)
- Conduct CSSRS interview
- Collect AEs
- Dispense study medication with a supply to last through the taper period. Provide the subject with dosing instructions. IP return and accountability.
- Begin 3-day taper (3 capsules on Day 29, 2 capsules on Day30, 1 capsule on Day31, or, if Day 28 dose is other than ganaxolone 900 mg or placebo, follow instructions in section 3.4.6)
- Perform physical examination

# 7.7 Post-treatment Follow-up Period (Days +29 to +71) – Cohort 6

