# 7.7.3 Third Post-treatment Follow-up Visit - 42 days After the Last On-treatment Visit (Day +71)

- The Follow-up Visit 3 should occur about 42 days after the Day 29 visit.
- CTNI to conduct interviews for HAMD17
- Perform EPDS
- Perform STAI6
- Assess CGI-I
- Review concomitant medications and therapies
- Collect vital signs (BP, pulse, temperature, RR)
- Collect urine sample for urinalysis, drug screen and urine pregnancy test
- Measure weight
- Conduct CSSRS interview
- Collect SSS
- Collect AEs

# Table 2. Schedule of Assessments - Cohort 6

Day	Day -14 to -1	Day 0 Admission	Day 1	Day 1 e	Day 2 f	Days 3 & 5	Day 4	Day 8	Days 10 & 13	Day 11	Day 15	Day 22	Day 29	Contraction (Section	17	100 BEA
VISIT	Screenin g		Baseline	Post-BL	Discharge & Outpatient	Safety call	V3 HAMD Call	V4 outpt	0-6-4-	V5 HAMD Call	V6 outpt	V7 outpt	V8 outpt	l st Follow- up	2 nd Follow- up	3 rd Follow- up
Informed consent	X															
Demographics, Medical History	X								10 10							-0
MINI neuropsychiatric interview	X											o				
Inclusion/Exclusion criteria	X	X														
Concomitant Meds and Therapy Review	X	X	X	X	X			X			Х	X	X	X	X	X
Admission to the unit		X														
Discharge from the unit					X			0			2	2 				N
Physical examination	X				X						X		X			
SAFER Interview (during screening)	X															
Vital signs (BP, Pulse, pO2, RR, temp)	X	X	X	X	X			X			Х	Х	X	X	X	X
Height (screening only) and weight	X	X		0.				0	2		X	5	Х	X	Х	X
ECGs	X	X		X	X			x			X	X	x	x		
Safety Laboratory Tests	X	X						x			X		X		X	
Neurosteroid level		X		X	X			X			X	X		X		
Urinalysis, Drug Screen and Pregnancy Tests	X	X		· .				X	2		Х	X	X	X	X	X
CSSRS	X	X	X	X	X			x	· · · ·		X	X	X	X	X	X
Record AEs		X	X	X	X	X		x	X		X	X	X	X	X	x
Randomization			X													
Start infusion (0h; 9 am $\pm$ 1h) a	-	)		X				0	3							0
End infusion (6h)	.a .c.	22		X							0 X0	07.			2	
PK sample collection b				X	X			X			X	X	X	X	1	Ť
HAMD17 c	X	X	X	x	X		x	X		X	X	X	X	X	X	X
CGI-I		)		X	X			X	1997 1997		X	X	X	X	X	X
CGI-S	X	27.	X								0 X0	02				-
EPDS	X		x	X	X			x			x	X	X	X	X	x
SSS			x	X	X			x			X	X	X	X	X	x
STAI6	X	54. 	X	X	X			x	a		x	X	x	X	X	x
Dispense medication/return accountability	a 75	C.Y			X			x	9		x	X	X			
Oral dosing (at dinner time)				X			ť	hroughout	the outpa	tient perio	d	11 75878 G	0.870			
Q15 min health checks & pulse ox d		X	through	out the inpa	tient period			[	•				1			

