# **12.0 APPENDICES**

Prohibited strong inhibitors	Prohibited strong inducers
Indinavir	Efavirenz
Nelfinavir	Nevirapine
Ritonavir	Barbiturates
Clarithromycin	Carbamazepine
Itroconazole	Enzalutamide
Ketoconazole	Glucocorticoids
Nefazadone	Modafinil
Saquinavir	Oxcarbazepine
Suboxone	Phenobarbital
Telithromycin	Phenytoin
Grapefruit juice	Pioglitazone
	Rifabutin
	Rifampin
	St. John's Wort
	Troglitazone

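### Exclusion 16 lifts the grapefruit, Seville orange, star fruit and citrus restriction at discharge, which covers all dosing in Cohorts 1-5 but only 1 of 31 oral dosing days in Cohort 6

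*Protocol*

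**What the plan says.** Criterion 16 excludes a subject for "Unwillingness to withhold grapefruit, Seville oranges, star fruit, or citrus derived products from diet between screening and discharge from the study unit". The synopsis copy has the same end point: "citrus derived products from diet between screening and discharge from the study unit". Neither copy distinguishes between cohorts. It is a willingness test, and Table 2 schedules the review of "Inclusion/Exclusion criteria" for Cohort 6 only at screening and on Day 0.

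A separate conduct rule sits in section 5.3.2: "The following classes of medications and treatments are prohibited during the study treatment period". Its list includes the strong CYP3A4 inhibitors and inducers of Appendix 1, where the only food is "Grapefruit juice". Section 5.3.1.3 likewise lets a subject continue her non-psychiatric drugs except "medications that are strong inducers or inhibitors of CYP3A4".

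The Cohort 6 home-dosing text (sections 3.4.5, 6.2, 6.3.2.2 and 6.5.2) deals with fatty food, water, the diary and alcohol. It mentions none of the foods in criterion 16.

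**The concern.** The end point suits a design in which all dosing happens on the unit. It does not suit Cohort 6, where most dosing happens at home. Followed as written, foods withheld throughout dosing in Cohorts 1-5 become permissible in Cohort 6 after the first of 31 oral doses. The drug has known sedation and dizziness (section 6.2.4), and these subjects are outpatients with infants.

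Exposure control is also at stake. Section 9.5 gives the study's purpose as finding a safe and well tolerated dose and exposure level. Cohort 6 fixes food intake to within 15 minutes of each capsule dose and draws PK samples at home-dosing visits on Days 8, 15, 22 and 29. Saying nothing about the restricted foods on those days sits poorly with that degree of control.

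Grapefruit juice is not the problem. Criterion 16 and section 5.3.2 overlap on juice and do not conflict.

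**Working it through.** The plan gives no figure of its own here, so the check is a day count from the dosing schedule.

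**Cohorts 1-5** (section 7.3.2)
- The infusion ends at +60 h and discharge is at +72 h.
- Margin: 72 − 60 = 12 h. The restriction covers all dosing.

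**Cohort 6, criterion 16** (sections 3.1, 3.4.5 and 7.0)
- The first oral dose is at about 7 pm on Day 1, and discharge is on the morning of Day 2.
- Full dosing is on Days 1-28 and the taper on Days 29-31. The tapers from 675 mg and 450 mg also last 3 days, so the count does not depend on dose.
- Oral dosing days: 28 + 3 = 31.
- Before discharge: 1, and 1/31 = 3.2%.
- After discharge at the target dose (Days 2-28): 27, and 27/31 = 87.1%.
- After discharge on taper: 3, and 3/31 = 9.7%.
- Total after discharge: 27 + 3 = 30, and 30/31 = 96.8%.

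The 6-hour Cohort 6 infusion is also covered by criterion 16. The count above concerns oral days only.

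**Cohort 6, grapefruit juice under section 5.3.2**

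Coverage depends on when the treatment period ends, which is not explicit. The section 7.7 heading reads "Post-treatment Follow-up Period (Days +29 to +71", the section 7.6 heading carries the outpatient treatment phase to Day 29, and the taper runs to Day 31.
- Treatment ends before Day 29: 28/31 = 90.3%.
- Treatment ends on Day 29: 29/31 = 93.5%.
- Treatment includes the taper: 31/31 = 100%.

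Appendix 1 names the juice, so whole grapefruit is covered at most by inference.

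**Length of the restriction in Cohort 6, with a 14-day screening period**
- Now: 14 (Days −14 to −1) + 1 (Day 0) + 1 (Day 1) = up to 16 days.
- Extended through Day 31: 16 + 30 = up to 46 days.
- With the 21-day screening period that section 7.1 allows on medical monitor approval: 21 + 2 = 23 days now, and 23 + 30 = 53 days if extended.

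**The case against.** The strongest objection is that no consequence is shown. Nothing in the documents says that Seville oranges, star fruit or ordinary citrus alter ganaxolone exposure. The one food the protocol classes as a strong inhibitor, grapefruit juice, is already barred. This stands: the percentages count days without a rule, not days of demonstrated risk.

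The second objection is about intent. The criterion may have been meant as an inpatient diet rule, since section 5.3.1.1 also ends its limit on new psychotherapy at discharge and applies to Cohort 6. Against that, Appendix 3 shows that Amendment 7, which set the present Cohort 6 regimen, moved inclusion 8, section 5.3.1.3 and section 5.3.2 to the treatment period and left criterion 16 alone. That looks like a leftover, but a deliberate choice cannot be excluded.

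The third is that the answer may lie in text not seen. Dosing instructions are given at discharge and at later visits and are not in the file. Section 1.2.1.3 and the consent pages were also absent from the copy reviewed. This limits the finding to the protocol's visible text.

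Finally, a home ban on all citrus products would be hard to monitor, because the visible diary items record only capsules and fatty food. That is fair, and it favours a shorter outpatient list. Existing safeguards also reduce the stakes: childcare and driving precautions (6.5.2), four safety calls (7.6.1) and dose reduction (6.2.4).

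**Conclusion.** The point holds as a minor one. Criterion 16 has a single end point that fits Cohorts 1-5 and does not fit Cohort 6, where 30 of 31 oral dosing days fall after it. On those days no visible rule covers whole grapefruit, Seville oranges, star fruit or other citrus products. No exposure increase is claimed, and its size could not be calculated from the documents.

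The conclusion assumes that the unseen dosing instructions and missing text do not already carry the restriction forward, so confidence is medium. The gain from correcting it is one clear diet rule for home dosing.

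**What to change.** In both copies of criterion 16, confine the discharge end point to Cohorts 1-5 and add, for Cohort 6, the last dose of study drug including taper. An anchor of this kind is already in use in inclusion 8: "Must agree to stop breastfeeding from start of study treatment to 45 days after end of study treatment".

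Because criterion 16 only tests willingness at entry, also add a sentence to section 6.5.2 telling Cohort 6 subjects to keep avoiding these foods until the last taper dose. State that end date directly. A cross-reference to section 5.3.2 would bring in its uncertain reach over the taper days. Appendix 1 needs no change.

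The cost is one phrase in two places, one new sentence and 30 more days of diet restriction (Days 2-31) in Cohort 6. If giving up ordinary citrus at home is judged too burdensome, limit the outpatient list to grapefruit, Seville oranges and star fruit.

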#### 4.3 **Reproductive Potential**

#### 4.3.1 **Female Contraception**

Sexually active females of childbearing potential should be using an acceptable form of contraception throughout the study period between screening and last follow-up visit.

Acceptable methods of contraception are:

- Intrauterine device plus condoms (If the subject has a hormone-releasing intrauterine device (IUD) this must have been in place for a minimum of 30 days)
- Double-barrier methods (e.g. condoms with spermicidal gel, foam or sponge, diaphragm with spermicidal gel, foam or sponge)
- Hysterectomy or tubal ligation at or after delivery

#### 4.4 Discontinuation of Subjects

A subject may withdraw from the study at any time for any reason without prejudice to their future medical care by the physician or at the institution. The investigator or sponsor may withdraw the subject at any time (e.g. in the interest of subject safety). The investigator is encouraged to discuss withdrawal of a subject from the investigational product with the medical monitor when possible. Withdrawn subjects who have not received IP will be replaced.

If the investigational product is discontinued, regardless of the reason, the evaluations listed for Day 4 are to be performed as completely as possible for Cohort 1-5, and Day 28 evaluations for Cohort 6. Whenever possible, all discontinued subjects should also undergo the protocol-specified follow-up. Comments (spontaneous or elicited), complaints or AEs reported by the subject must be recorded in the source documents. The reason for discontinuation and the date and time of discontinuation of the investigational product must be recorded in the case report form (eCRF) and source documents.

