### 6.2.6 **Unblinding the Treatment Assignment**

The treatment assignment must not be broken during the study except in emergency situations in which the identification of the investigational product is required for further treatment of the subject. The investigator should contact the medical monitor before unblinding, if possible. However, this should not delay unblinding in case of an emergency. The investigator should contact the medical monitor has been unblinded.

In the event that the treatment assignment is broken, the date, the signature of the person who broke the code, and the reason for breaking the code are recorded on the source documents. Upon breaking the blinding, the subject is withdrawn from the study, but should be followed up for safety purposes. Any code-breaks that occur must be reported to the Contract Research Organization (CRO) and sponsor.

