### 7.3.2 **During Infusion (Days +1 to +4)**

- Start bolus/infusion in the morning of Day +1 (0h) after baseline assessments are completed
- CTNI to conduct interviews for HAMD17 (+12h, +24h, +48h, +60h, +72h)
- Conduct interviews for CGI-I (+12h, +24h, +48h, +60h, +72h)
- EPDS (+60h)
- STAI6 (+12h, +24h, +48h, +60h, +72h)
- Collect AEs
- Collect ECG (+12h, +24h, +48h, +72h)
- Collect VS (BP, pulse, respiratory rate, pulse oximetry, temperature): (+4, +8h, +12, +18h, +24h, +32h, +40h, +48h, +56h, +60h, +72h)
- Collect SSS (+8h, +32h, +56h, +72h)
- Collect pharmacokinetic samples (+12h, +24h, +48h, +72h)
- Record concomitant medications
- Lower the infusion rate to half what was prescribed for the cohort (for example, lower the infusion rate from 4 mg/h to 2 mg/h) (+48h)
- Collect safety laboratory tests (+48h)
- Collect neurosteroid level (+48h)
- End infusion (+60h)
- Collect urine sample for urinalysis, drug screen and urine pregnancy test (+72h)
- Conduct CSSRS interview (+12h, +36h, +60h, +72h)
- Perform a physical examination (+72h)

- Stop monitoring of pulse oximetry and Q15 min health checks (+72h)
- Discharge subject (+72h)

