#### Specific timepoints for assessments on days +1, +2, +3 and +4: - Cohorts 1-5

PK samples: +12h, +24h, +48h, +72h HAMD17: before start of infusion, +12h, +24h, +48h, +60h, +72h all done by CTNI CGI-I: +12h, +24h, +48h, +60h, +72h CGI-S: before start of infusion EPDS: before start of infusion, +60h STAI6: before start of infusion, +12h, +24h, +48h, +60h, +72h ECG: +12h, +24h, +48h, +72h Vital Signs: (BP/P/pO2/RR/Temp): before start of infusion, +4, +8h, +12, +18h, +24h, +32h, +40h, +48h, +56h, +60h, +72h SSS: before start of infusion, +8h, +32h, +56h, +72h CSSRS: before start of infusion, +12h, +36h, +60, +72h Safety laboratory tests and neurosteroid level: +48h Urinalysis drug and pregnancy test: +72h Physical examination: +72h AEs and concomitant medications are collected throughout the inpatient stay.

Q15min health checks are done from the time of admission to the time of discharge. Pulse oximetry (pO2) must be monitored throughout the infusion, including during the night when the subject is sleeping. The subject should be awakened if pulse oximetry falls < 91%.

The following priority order will be in effect when more than 1 assessment is required at a particular time point: 1) HAMD17 2) CGI-I/CGI-S 3) EPDS 4) STAI6 5) SSS 6) CSSRS 7) vital signs 8) ECG 9) safety labs and neurosteroid level 10) PK sample 11) neurosteroid level 12) urinalysis drug screen and pregnancy test 13) physical examination

Day 11 and Day 34 visits have visit windows of  $\pm$  3 and  $\pm$  5 days, respectively

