## 7.7.1 First Post-treatment Follow-up Visit - 7 days After the Last On-treatment Visit (Day +36)

- The Follow-up Visit 1 should occur about 1 week after the Day 29 visit.
- CTNI to conduct interviews for HAMD17
- Perform EPDS
- Perform STAI6
- Assess CGI-I
- Review concomitant medications and therapies
- Collect vital signs (BP, pulse, temperature, RR)
- Collect ECG Collect neurosteroid level
- Collect a pharmacokinetic sample
- Collect urine sample for urinalysis, drug screen and urine pregnancy test
- Measure weight

- Conduct CSSRS interview
- Collect SSS
- Collect AEs
- IP return and accountability

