### 9.5.8 Efficacy Analyses

### 9.5.8.1 Primary Endpoint

The primary efficacy endpoint will be HAMD17 total score change from baseline to 60 hours post-infusion (on Day 3) for Cohorts 1-3 and to Day 29 for Cohort 6. The primary analysis in each cohort will be done using the mITT set. Although the trial is not powered for inferential analysis and there is no consideration for control of type 1 error across multiple cohorts, a clinically meaningful numeric difference in means of 3-4 points between ganaxalone and placebo treatment groups would be considered an indication of efficacy and will be the most influential outcome in the overall assessment of the efficacy of ganaxalone in treating PPD.

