### 8.2 Other Definitions

#### +72h

72 hours after start of infusion (0hr) based on visit window. If a subject is discontinued from the study during the inpatient treatment phase (Day 1 through Day 4), all assessments scheduled at +72h will be collected at the time of study exit, but the assessments will be allocated to analysis visits based on visit windows detailed in Section 8.4.

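### Protocol 4.4 does not ensure that the primary HAMD17 (+60h in Cohorts 1-5, Day 29 in Cohort 6) is collected after study drug is stopped

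*Protocol*

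**What the plan says.** - **Stopping rule.** Protocol 4.4 applies whenever investigational product is discontinued, for any reason. In that case "the evaluations listed for Day 4 are to be performed as completely as possible for Cohort 1-5, and Day 28 evaluations for Cohort 6". It adds: "Whenever possible, all discontinued subjects should also undergo the protocol-specified follow-up". Neither sentence says when the evaluations are to be done.
- **Primary endpoint.** Protocol 9.5.8.1 defines it as "HAMD17 total score change from baseline to 60 hours post-infusion (on Day 3) for Cohorts 1-3 and to Day 29 for Cohort 6". SAP 12.5.1 applies the +60h time point to all intravenous-only cohorts.
- **Cohorts 1-5 schedule.** Protocol 7.3.2 has "CTNI to conduct interviews for HAMD17 (+12h, +24h, +48h, +60h, +72h"). The +60h rating belongs to Day 3, and +72h is the Day 4 discharge list. Follow-up visits are on Days 11 and 34.
- **Cohort 6 schedule.** Protocol 7.6 and Table 2 end the on-treatment visits with Visit 8, Day 29 ±3 days, which includes a HAMD17. There is no Day 28 visit; Day 28 is only the last full-dose day. In Protocol 7.7.1, "The Follow-up Visit 1 should occur about 1 week after the Day 29 visit", that is, Day 36. The other two follow-up visits are on Days 57 and 71.
- **Exit assessments.** For a woman discontinued from the study in the inpatient phase, SAP 8.2 says that "all assessments scheduled at +72h will be collected at the time of study exit". They are then assigned to an analysis window by actual time (SAP 8.4).
- **Missing data.** The mixed model in SAP 12.5 assumes missing-at-random. The same section says that women doing poorly may be likelier to miss assessments, but makes its placebo-based multiple imputation optional.

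**The concern.** The rule for what is collected after drug is stopped points at visits other than the primary one. In Cohorts 1-5 it names the list 12 hours after the primary rating. In Cohort 6 it names a visit that is not in the schedule. Sites must guess which list is meant and when to carry it out, and one plausible guess (do it now, at stopping) usually gives no rating at the primary time point.

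Adverse events and lack of efficacy are listed reasons for discontinuation (Protocol 4.4.2), so stopping may be related to outcome. A woman who stops stays in the mITT set once she has one post-randomization efficacy assessment. If her primary value is missing, the model supplies it from her earlier ratings and from women still under observation. With 10-30 women per cohort at 1:1, an arm has about 5-15 women, so one missing value is 1/15 to 1/5 of an arm (7-20%). The outcome affected is the 3-4 point mean difference that both documents call the most influential for judging efficacy.

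**Working it through.** The plan gives no stop rate, standard deviation or power, so there is no planned figure to reproduce. The check sets Protocol 4.4 against the schedules and the SAP 8.4 windows.

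**Inputs**
- +60h window: 3480 to <3960 minutes (SAP 8.4). 3480/60 = 58 h and 3960/60 = 66 h. The +72h window starts at 66 h.
- Day 29 window: Study Days 26-32 (SAP 8.4).
- Infusion length 60 h; Cohort 6 full dosing Days 1-28, taper Days 29-31.

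**1. Cohorts 1-5, evaluations done at stopping.** A rating made at the stop time is assigned as follows.

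| Stop time (h) | Window |
|---|---|
| 12 | +12h |
| 24 | +24h |
| 36 | +40h |
| 48 | +48h |
| 57 | +56h |
| 58 to 60 | +60h |

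Only stops in the last 60 − 58 = 2 hours reach the primary window: 2/60 = 3.3% of infusion time. This is a share of time, not a probability, because stops need not be spread evenly.

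**2. Cohorts 1-5, evaluations done on calendar Day 4.** A rating at 72 h falls in the +72h window. The primary value then comes only from the scheduled +60h rating in 7.3.2, which 4.4 does not mention.

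**3. Cohort 6, evaluations done at stopping.** The exit rating is in Days 26-32 only for stops on Days 26-28: 3/28 = 10.7% of full-dose days. Counting the taper, Days 26-31 give 6/31 = 19.4%.

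**4. Cohort 6, evaluations done on calendar Day 28.** Day 28 lies within Days 26-32, so the rating supplies the primary value.

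**5. Follow-up visits.** With the Day 36 visit at its earliest, 36 − 3 = Day 33, which is outside Days 26-32. In Cohorts 1-5 the earliest is 11 − 3 = Day 8. Neither can supply the primary value when held at the stated days.

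**6. Illustration, assumed values only.** Suppose a fraction d of active-arm women stop, truly have no benefit, and are modelled as having the same benefit as the rest, with no offsetting stops on placebo. A modelled difference Δ then corresponds to a true difference of Δ(1 − d).

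| d | Δ = 3 | Δ = 4 |
|---|---|---|
| 5% | 2.85 | 3.80 |
| 10% | 2.70 | 3.60 |
| 20% | 2.40 | 3.20 |
| 30% | 2.10 | 2.80 |

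Over this range the number of women concerned per arm runs from 5 × 0.05 = 0.25 to 15 × 0.30 = 4.5.

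**The case against.** The strongest reply is that 4.4 adds evaluations and cancels none. The +60h rating in 7.3.2 and the Visit 8 rating in 7.6.7 are not conditional on still receiving drug, so a woman who stops but stays in the study remains scheduled for them. The follow-up sentence in 4.4 is also not expressly limited to post-treatment visits. SAP 8.2 concerns discontinuation from the study, which it ties to a Study Exit page, not every stop of drug. Day 28 is one day from Visit 8 and inside its window. The SAP does describe a placebo-based sensitivity analysis, efficacy is hypothesis-generating, and Protocol 1.2.1.4 reports no adverse-event discontinuations so far in Cohorts 1-3.

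All of this stands, and it limits the point. A reader might infer that the primary value is missing by design for every woman who stops; the documents do not support that. They leave collection unassured, because 4.4 neither requires the primary rating after stopping nor fixes the timing of what it does require.

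Three further inferences should also be resisted.
- **Half of Cohort 6 stop days lose the value.** If follow-up is counted from stop day s, the nominal visits s+7 and s+28 fall in Days 26-32 for s = 19-25 and s ≤ 4, and the exit visit itself does for s ≥ 26. Days 5-18 (14 of 28) are left uncovered. That ignores the ±3-day windows. With them, s+7 can reach the window from s = 16 (16 + 10 = 26) and s+28 up to s = 7 (7 + 25 = 32), so only Days 8-15 (8 of 28) can never reach it. Section 7.7.1 in any case ties follow-up to the Day 29 visit.
- **Most inpatient exit ratings are wasted.** Windows with a scheduled HAMD17 cover 5 + 7 + 8 + 2 = 22 of the 60 hours, so 38 hours map elsewhere. This does not measure loss of the +60h value.
- **Emergency unblinding belongs to the same gap.** Protocol 6.2.6 says: "Upon breaking the blinding, the subject is withdrawn from the study, but should be followed up for safety purposes". That is a separate rule, and no contradiction with 4.4 is shown.

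**Conclusion.** The point holds as a gap in what the plan secures. Section 4.4 does not ensure the primary HAMD17 after drug is stopped, its Cohort 6 reference matches no scheduled visit, and its timing is undefined. If the evaluations are done at stopping, the exit rating serves the primary analysis only for stops in the last 2 of 60 infusion hours or on Days 26-28 of full dosing. On the calendar-day reading Cohort 6 is covered, while Cohorts 1-5 still depend on the separately scheduled +60h rating.

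The size of any bias is unknown. The table in step 6 shows only that a stop rate of 20% with no benefit among those who stop would move a 3-4 point difference to 2.4-3.2. A reader might take that as an estimate, but the documents give no stop rate, no outcome after stopping and no direction of imbalance. Cohort 6 is the main exposure, with 28 days of mostly outpatient dosing. The Cohort 3 safety statement rests on 13 women, and stops for reasons other than adverse events are not reported in that section.

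The change is worth making because it affects which data are collected and lessens reliance on an assumption that the SAP itself questions.

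**What to change.** 1. In Protocol 4.4, replace the Day 28 reference with the Visit 8 (Day 29) evaluations, and state for both designs whether the evaluations are done at stopping or on the scheduled day. Reconcile 4.4 with Protocol 7.6.7, Table 2 and SAP 8.2.
2. State that a woman who stops drug but has not withdrawn consent is still asked for the CTNI-rated HAMD17 at its scheduled primary time, in addition to any exit rating: +60h in Cohorts 1-5, and Day 29 in Cohort 6 by the call format already used for Visits 3 and 5.
3. Keep the SAP 8.4 allocation of exit ratings by actual time. Moving them to the nearest scheduled time point would mislabel them; a 36 h rating, for example, would be analysed as +24h or +48h. If an exit rating and the added rating share a window, SAP 8.4 already takes the latest.
4. Leave Protocol 6.2.6 unchanged.

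The cost is protocol wording and one extra rater contact for each woman who stops. Some women will decline, so the gap narrows but does not close.
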